All serious adverse events will be notified by the principal investigator to the regulatory agencies, ethical review committees and Data Safety Monitoring Board (DSMB) within 24 hours. However, the investigational team will report clusters of AE (at least three within one week) to the DSMB periodically for further evaluation.

Data safety monitoring board (DSMB)

The study will be monitored by a DSMB constituted by icddr,b with input by Ethical Review Committee (ERC). The DSMB will include representation outside of icddr,b. The DSMB is expected to convene once prior to the start of the study after ethical and regulatory approval of study protocol. The DSMB will convene meetings at the time of starting the study, near the middle of the study and at the study completion. The DSMB will be responsible for establishing study stopping rules. Immunogenicity data will not be available for DSMB meetings as all blood specimens will be analysed after the completion of study field activities.

Ethical Assurance for Protection of Human rights

Justification for involving a vulnerable population

Infants will be enrolled at 6 months of age. Enrolment at this early age is required as the study is assessing the immunogenicity of MR vaccine that is recommended at this age during outbreak response activities in response to outbreaks with infants affected at age < 9 months (age for measles routine vaccination). In addition, some researchers have suggested that the first measles vaccination should be given at a time point earlier than 9 months of age, based on the reports that infants born to mothers with vaccine induced immunity against measles may have lower concentrations of maternal antibodies and may lose protection by maternal antibodies at an earlier age.(26, 35, 36) All infants will be administered MR vaccine at age 9 months and some will receive an earlier dose at 6 months. Routine MR second dose will be given at 15 months as per current national immunization schedule endorsed by MoHFW in Bangladesh.

Potential benefits and compensation to participants

Participants will receive all recommended vaccines as per the vaccination schedule of Government of Bangladesh. EPI vaccines will be supplied by the government of Bangladesh. If a child has missed a routine vaccine dose (Pentavalent or polio) that she or he needed to get before the age of 6 months, parents will be encouraged to get their child vaccinated for other routine childhood vaccines.

Some infants in the study will be randomly selected (study arm A) to receive MR vaccine at 6 months, 3 months earlier than the current age (9 months) for MCV1. This will provide early protection against measles and rubella to those infants who seroconvert. All infants will also receive MR vaccine at 9 months as study participants. MR dose scheduled to be administered at 9 months as part of routine immunization will be cancelled. Children then will continue on to receive measles vaccine at 15 months per routine immunization schedule.

During study visits, participants will be examined by study physicians. They will assess infants' growth and development. In addition, participants will be offered advice on diagnosis and treatment of any other illness they experience during the study period. Treatment related cost will be covered by the study.

Potential risks to participants

The potential risks and discomfort to participants stem from blood collections and adverse reactions to MR vaccine.

Immunogenicity of the MR vaccine can only be assessed from testing the blood specimens. Multiple blood draws would be necessary as immunogenicity is measured by determining the change in antibody titers. Moreover, enrolled infants may have maternal antibodies against measles and rubella acquired transplacentally. The first blood draw at 6 months (for infants in both study arms A and B) will establish the baseline maternal antibody titers. The titers are assumed to decay at a fixed rate.

Subsequent blood draws at 9 and 11 months will aid in assessing immunogenicity of MR vaccine as per the primary and secondary objectives. Collecting blood samples from infants in Arm B would help us determine what proportion of infants are additionally protected at 9 months when compared to infants in Arm A. It would also help us determine the rate of background exposure to measles and rubella circulation between 6 and 9 months (only 50% of rubella cases are symptomatic).

The minimal amount of blood necessary for testing is 1 ml. The most common effect of blood draws is pain at the site of collection. In order to minimize the discomfort and risks associated with blood draw, blood from infants will be drawn only by qualified staff experienced in collection of blood in infants. Sterile equipment and technique and alcohol swabs will be used to reduce the risk of infection from blood draw. Pressure will be applied at the site of blood draw to minimize bleeding from the site of blood draw.

MR vaccine (dose is 0.5ml) per WHO EPI immunization guidelines will be administered following all safety norms. The most common side-effect of MR vaccine injection is pain and redness at the site of administration. The site will be used for monitoring of local reactions.

MR vaccine may have some traces of neomycin. Rarely participants may react to these substances through these reactions. One serious but extremely rare adverse effect to measles vaccine is anaphylaxis. The risk is extremely low - 1 in 3.5 million doses administered(4). Overall, adverse events, with the exception of anaphylactic reactions, are less likely to occur after receipt of a second dose of measles containing vaccine.

It is important to recognize the early symptoms of anaphylaxis and treat such cases immediately. Therefore all infants who receive study vaccine dose will be observed for 30 minutes by medical officer and if any signs of anaphylactic reaction are noticed the medical officer will initiate treatment on the site. Treatment will be free of charge. This child will not receive future MR vaccine doses. Special notes will be made in his medical card. Although we do not expect any additional side effects the 6 months infants will be followed for 48 hours after receipt of the first MR study dose because they receive MR vaccination before the age of routine vaccination in Bangladesh. Most common adverse events in infants at 6 months after administration of measles containing vaccine are fever, mild rash, redness and swelling of injection site. Most adverse effects are mild and self-limited.

Forty eight hours after vaccine administration at 6 month a study staff will visit respondents at their home to monitor and document any adverse effects following immunization.

All costs will be provided by the study for infants who experience severe adverse events in this study.

Participant Privacy

Personal identifiers, including birth date and sex will be collected and recorded on study case report forms (CRFs) and each participant will be given a study identification card with Current Identification Number (CID)/Registration Identification Number (RID) number. Other information collected by study staff and recorded on a linking document containing the study participant identifier will include the name of the participant, name of the parents, CID number, location/address of residence, and other identifiers important for ensuring follow-up throughout the study period. The CID number on the card and the linking document provides the link between the participant and his/her study information. Although this linking document will be stored separately from the study CRFs containing study data, a potential risk for “loss of confidentiality” does exists.

To avoid this risk, participants will be assigned a unique study participant number that will be used to identify the participant and link, using the linking document, an individual to his/her study data and/or biological specimens. This linking document will be destroyed once data are finalized. Whenever feasible, use of identifiers, such as name and addresses, will be avoided and the unique study participant numbers will be used instead. Paper-based records (i.e., CRFs) will be kept in a separate, secure location with controlled access and will only be accessible to personnel involved in the study. Computer-based files will only be made available to personnel involved in the study through the use of access privileges and passwords. Individual participants will not be identified in any study related reports, and all study results will be reported in aggregate only.

Biological specimens (serum) will be identified by study participant number, and specimen collection date. Following collection, the specimens will be processed according to specimen handling/processing guidelines and stored at Matlab Health Research Centre. Serum specimens will be shipped to the United States Centers for Disease Control and Prevention (CDC). The links between study data and the study specimens will not be destroyed, but no personal-identifying information associated with the study will be stored on site with the specimens.

Institutional Review Board (IRB) and ethical review

The protocol with letters of consent and other associated appendices will be reviewed and approved by the Ethical Review Committee (ERC) and Research Review Committee (RRC) at the icddr,b before any participants are enrolled. The ERC and RRC at the icddr,b will be responsible for oversight of the study.

All participants will be below the legal age of consent as participants will be enrolled at 6 months of age. Parents or legal guardians of potential participants will be informed that their participation in this study is strictly voluntary and that they are free to withdraw from the study at any time. A signed consent form will be obtained from the parent or legal guardian of the participant. Irrespective of literacy status of parents the consent form will be explained in the presence of a witness not directly related to the study. The consent form will describe the purpose of the study, the procedures followed, confidentiality of recorded information, and the risks and benefits of participation. Consent forms will be translated from English to Bangla, the local language. A copy of the consent form will be given to the parent or legal guardian of the participant and this would be noted in the participant record. Any subsequent modifications to the protocol will be submitted to the ERC and RRC at the icddr,b for additional approval.

Participant confidentiality procedures

All CRFs, laboratory specimens and other reports including reports of adverse events will be identified by PID to maintain participant confidentiality. No identifiers will be recorded on CRFs, other study reports and laboratory specimens. All records will be stored in a locked cabinet. All electronic records will be password protected. Access to paper and electronic records will be restricted to study staff and investigators.

The manufacturers of vaccines used in the study may use study data and results for their vaccine product regulatory files and may also present this data and study results to regulatory agencies. No identifiers will be shared with vaccine manufacturers or regulatory agencies. All participant data will be identified by PID.

Use of animals

Not applicable.

Dissemination and use of findings

icddr,b and CDC investigators will produce a detailed report of the study findings as well as an executive summary. These findings will be shared with all stakeholders including the government of Bangladesh EPI program, through a dissemination meeting. In addition, a manuscript of the findings will be submitted to peer reviewed journals for publication.

Collaborative Arrangements

This study includes two partners with the following roles in the study:

1. International Centre for Diarrhoeal Diseases Research, Bangladesh (icddr,b)
 - Collaborate in the development of the study protocol and submission through ethical and scientific committees in Bangladesh.
 - Select study sites and study staff and develop a budget for study implementation
 - Develop standard operating procedures, study forms and training material. Conduct training and supervise study staff.
 - Carry out implementation of the study procedures and coordinate logistics for sample collection, processing and storage; as well as study vaccine storage and administration.
 - Record and provide treatment for potential adverse events developed during the study.
 - Enter data collected in questionnaires into a database for future analysis.
 - Collaborate with CDC investigators in the analysis, interpretation and writing of the study results for study reports and manuscripts to be published in peer review journals
2. Centers for Disease Control and Prevention, Atlanta, GA, USA
 - Design of the study and provision of funding for its implementation
 - Submission of the protocol for CDC ethical clearance
 - Provide support in the training of study staff
 - Monitor study implementation through visits to the study sites in coordination with the icddr,b
 - Test serum specimens for the determination of antibodies against measles and rubella (laboratory at the Division of Viral Diseases) and enter laboratory data into an electronic database
 - Lead data analysis, interpretation of the results and writing detailed reports and manuscripts for publication in peer reviewed journals in collaboration with icddr,b investigators

Facilities Available

Field site

The study will be carried out in rural area at Matlab, Bangladesh. CDC and icddr,b (The International Centre for Diarrhoeal Disease Research, Bangladesh) have previously collaborated to conduct several clinical trials including polio, measles and rubella and rotavirus trials at this site.

Clinical facilities

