Prior to the development and widespread use of measles vaccines, measles was estimated to cause between five and eight million deaths annually. In the pre-vaccine period, >90% of individuals were infected by 10 years of age. Wide scale introduction of safe and effective measles vaccines has greatly reduced the burden of this disease. For example, the recent global measles update shows that during 2000–2014, the number of annually reported measles cases worldwide decreased 69%, from 853,479 to 267,482, and measles incidence decreased 73%, from 146 to 40 cases per million population. Although the number of annually reported measles cases worldwide decreased due to measles vaccination programs, measles continues to cause high morbidity and mortality among children. It is one of the leading causes of vaccine preventable childhood death with annual estimated measles deaths in 2014 reaching 114,900 (1).

Measles is an acute viral respiratory illness. Measles is caused by single-stranded, enveloped RNA virus with one serotype. Measles virus is highly infectious (reproductive rate of 12-18) and occurs only in humans; measles virus is transmitted by aerosolized respiratory droplets and by direct contact (4). It is characterized by fever and malaise, cough, coryza, and conjunctivitis followed by maculopapular rash. The rash spreads from the head to the trunk to the lower extremities. The incubation period ranges from 7 to 21 days. An infected person is contagious during the time from 4 days to 4 days after the rash appears. The severity of measles depends on a number of host and environmental factors. Infants have more severe and longer duration of measles illness, with high mortality.(7, 12) Children under 5 years of age who live in overcrowded conditions or who are malnourished (have vitamin A deficiency), and children with immunological disorders are at higher risk for developing complications such as pneumonia, diarrhoea, encephalitis, and blindness or death. In some developing countries, case-fatality rates among young children may reach 5–10%.(2, 3)

Rubella

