Rubella is an enveloped single-stranded RNA virus. Humans are the sole host of the virus. Rubella is a mild, self-limited illness that usually occurs during childhood. The rubella rash occurs in 50-80% of infected persons. Children develop few or no symptoms; however, adults may have a prodrome (1-5 days) of low-grade fever, headache, malaise, mild coryza and conjunctivitis. Postauricular, occipital and posterior cervical lymphadenopathy is characteristic, and typically precedes a maculopapular, erythematous and often pruritic rash. Rubella is transmitted through direct or droplet contact from nasopharyngeal secretions. The incubation period of rubella is 12-23 days. Persons with rubella are most infectious when rash is erupting, but they can shed virus from 7 days before to 7 days after rash onset. Up to 70% of adult women with rubella may develop arthralgia or arthritis. Complications of rubella include thrombocytopenic purpura and encephalitis. Postinfectious encephalitis occurs in approximately 1/6000 rubella cases; however, in the Pacific Islands, Hong Kong and Tunisia, there has been a documented increase in frequency to 1:500.(13, 14) During 2000-2014, the number of rubella cases worldwide declined by 95% from 670,894 (in 102 countries) to 33,068 (in 161 countries) (15).

Congenital rubella syndrome

Rubella infection during early pregnancy may result in serious consequences, including miscarriages, stillbirths, and a constellation of severe birth defects in infants known as congenital rubella syndrome (CRS). The risk of congenital infection and defects is highest during the first 12 weeks of gestation and decreases after the 12th week of gestation; and defects are rare after the 20th week of gestation. The most common congenital manifestations are sensorineural hearing impairment, ophthalmologic (i.e., cataracts, pigmentary retinopathy), and cardiac (i.e., patent ductus arteriosus, peripheral pulmonic stenosis) (5, 6, 14)

Rubella /CRS control and elimination

High rubella vaccine coverage has significantly reduced rubella and CRS in both developed and developing countries. In 2014, a total of 33,068 rubella cases were reported to WHO from 102 countries, a 95% decrease from the 670,894 rubella cases reported in 2000 from 161 countries. In the Americas, the last endemic rubella and CRS cases were reported in 2009, and the region was declared free of endemic rubella virus transmission in April 2015.(15)

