- Identification of immunodeficiency disorder, bleeding disorder or another medical condition for which continued participation, in the opinion of the investigator, would pose a risk to the participant to continue in the study
- Receipt of immunosuppressive medications
- Allergic reaction to a prior dose of measles or rubella containing vaccine or its contents necessitating withdrawal
- Premature termination of the study

- The participant has moved to another area outside of Matlab and is not available for follow up visits
- In case of a withdrawal from study, the local investigator should talk to a parent and document reasons why they are withdrawing, and document any adverse events or conditions that necessitate withdrawal of a participant from the study.

Termination of study

There seem to be no anticipated reasons that may result in suspension or termination of the study.

Nevertheless, there are possible causes that may warrant termination of study:

- Unexpected high number of severe adverse reactions related to use of MR vaccine or any other safety concern then any ethical committee overseeing the study, Ministry of Health or CDC can terminate the study for any safety reasons.
- A large measles or rubella outbreak in the community
- An outbreak response immunization activity with MR vaccine targeting infants aged 6 months and older in the area in response to a large measles or rubella outbreak

Measles or rubella diagnosis; measles or rubella outbreak in the community

If during the course of the study, an infant is diagnosed with a laboratory confirmed measles or rubella infection – it will not be a reason for discontinuation. If an infant is diagnosed with measles or rubella study staff will make sure that the child is non-infectious (at least 4 days after rash onset) then parents will be asked to bring the child to study site for a follow up visit

Concomitant medications and vaccines

- There will be no restrictions on the use of medications or treatments for concomitant diseases. If child is prescribed an immunosuppressive medication then the child will be excluded from the study.
- Parents will be encouraged to get their child vaccinated for other routine childhood vaccines; upon completion of the study, all parents will be reminded to take their child to their assigned vaccination centre to receive a second dose of routine measles vaccine at 15 months of age

Adherence to group assignments

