1. The study physician will complete the study questionnaire and examine the participant
2. 1 ml of blood will be drawn from each infant (both study arms A and B).
3. Study vaccine will be administered to ALL infants (both study arm A and B). The participant will be observed for 30 minutes to monitor for any adverse reactions
4. Schedule the next visit at 11 months of age

MR vaccination at 9 months is now routinely given in Bangladesh. Therefore, there will be no follow-up household safety monitoring visit after the 9 month MR dose during the study.

Temporary exclusion

- Participants who meet temporary exclusion criteria for vaccination will be excused for the day and will be requested to return several days later, but as long as their age is 9 months, +/- 7 days. A note will be made in the study log book.

Study site visit at 11 months of age. Blood draw and Study exit.

This visit will be the third and last planned study visit for participants. During this visit, the following procedures will be conducted:

1. The study physician will complete the follow up form and examine the participant
2. 1 ml of blood will be drawn from each infant (from both study arms A and B).
3. At study exit, parents will be reminded to bring their child to the fixed site clinic or another EPI facility to receive their second dose of measles vaccine according to the new EPI schedule (at age 15 months).

Laboratory evaluations

Clinical Laboratory Evaluations

No clinical laboratory evaluations will be offered in this study. Laboratory assays described in the protocol are for research purposes only and laboratory results will not be used for clinical diagnosis.

Special Assays or Procedures

Blood samples will be obtained at 6 months from all infants (at enrolment) and mothers and tested for measles and rubella antibodies. The baseline levels will identify infants who have transplacentally transferred maternal antibodies been exposed to natural measles infection before the enrolment to the study. The mothers' antibody levels will be determined and they will be classified as "susceptible" or "protected" (seroprotection definitions will be the same: titer of ≥ 120 mIU/mL for measles and rubella >10 mIU/mL).

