For participants in the study group A, the immune response to the 6 month MR dose will be measured at 9 months (blood drawn during the second visit) to evaluate both the proportion seroconverting (from negative to protected), 4-fold or greater increase in antibody titers among pre-vaccination seropositives, after adjusting for decline in maternal antibodies, as well as the magnitude of the immune response (expressed as geometric mean titers of the antibody response). The rate of decay of maternal measles and rubella antibodies will be calculated in infants in arm B based on the difference of antibody levels measured at 6 months (baseline) and 9 months. We will incorporate the model of maternal measles and rubella decay for infants in arm A to measure post-vaccine antibody levels and impact of the maternal

antibody to immune response in infants who had measles or rubella antibodies at enrolment. In the recently published study from Bangladesh, baseline measles virus serum neutralizing antibody seroprotection and anti-rubella virus IgG seroprotection at 9 months of age was low (0.42-1.25% and 0-0.42%, respectively) (21). If during this study, we determine that most children have no detectable levels of maternal measles or rubella antibodies at 6 months it would be impossible to calculate the decay. In this case, we will refer to antibody decay rates reported elsewhere (29, 30).

THE FOLLOWING CHANGES ARE MADE TO THE PROTOCOL:

Since the inception of the project and completion of the field data collection a newer assay, multiplex bead assay (MBA) for measles and rubella has been developed. It has been validated by the CDC measles and rubella laboratories.

Multiplex Bead Assay (MBA) for Serum Antibody Detection of Measles and Rubella

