A major limitation of many studies in which mother-infant paired serum samples were tested, was ascertainment of mothers' past measles or rubella vaccination or measles and rubella natural infection status. Some authors used age (i.e., year of birth, born in pre- measles or rubella vaccination era) as a proxy for determining the past vaccination or disease status. One recent study minimized recall bias as the researchers ascertained mothers' status (vaccine induced or post-infection antibodies) by reviewing their medical charts. [4]

Primary analytical approach

Intention-to-treat (ITT) analysis will be conducted on all enrolled participants who are randomized and receive two measles-rubella vaccines (at 6 and 9 months, study arm A) or one measles-rubella vaccine dose (at 9 months, study arm B).

Children who are seropositive ($\geq 1:120$ mIU/mL) for measles before vaccine administration (at 6 months of age, study arm A; at 9 months, study arm B) will be included in the ITT analyses and will be included in the safety analysis. Similarly, children who are seropositive (≥ 10 IU/mL) for rubella before vaccine administration (9 months of age) will also be included in the ITT analyses.

To evaluate primary and secondary objectives, the analysis will be restricted to participants who

- Have not withdrawn consent for receipt of MR vaccine and follow-up evaluations since enrolment
- Have adequate blood specimen for serological analysis from the enrolment visit, and
- Have adequate blood specimen for serological analysis from study site visits at 6, 9 and 11 months of age (For presence of maternal measles and rubella antibodies – 6 months, seroconversions: 9 months of age and 11 months)

Secondary analytical approach

In addition, we will also perform a per protocol analysis.

To evaluate primary objective, per protocol analysis will be restricted to participants who

- Have not withdrawn consent for receipt of vaccines and follow-up evaluations since enrolment
- Have adequate blood specimen for serological analysis from each visit within 3 days of 6, 9 and 11 months of age, and
- Have received all scheduled vaccines within 3 days of scheduled visit date

Using the above described primary analytical approach we will

- Compare the proportion of participants demonstrating immunogenicity in response to measles and rubella vaccines across study arms and use chi-square test to test for statistical significance across study arms.

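### The 4-day wait before recalling an infant with measles or rubella is up to 3 days short for rubella, on the protocol's own shedding period (a minor safety point)

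*Combined protocol and SAP*

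**What the plan says.** The section on measles or rubella diagnosis and outbreaks in the community states that a laboratory-confirmed infection with either virus does not end an infant's participation. For an infant diagnosed with either disease, "study staff will make sure that the child is non-infectious (at least 4 days after rash onset", and the parents are then asked to bring the child to the site for a follow-up visit. The bracket is the only test of non-infectiousness given, and it serves both diseases.

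The Background gives the two diseases different periods:

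- Measles: "An infected person is contagious during the time from 4 days to 4 days after the rash appears". The start of the period is garbled, but its end is clear.
- Rubella: "Persons with rubella are most infectious when rash is erupting, but they can shed virus from 7 days before to 7 days after rash onset".

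No other section of the protocol states a rubella interval for site visits.

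**The concern.** A rule that fits measles appears to have been applied to rubella without adjustment. A child with rubella could be called in on day 4, 5 or 6 after the rash starts, pass the stated test, and still be within the time when the protocol says virus can be shed.

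The people who might be exposed are other study families. Infants arrive at 6 months with no MR dose, and Arm B infants are still undosed when they arrive at 9 months. Mothers attend for a blood draw at enrolment, and pregnancy is not among their listed exclusions. The Background describes the serious consequences of rubella in early pregnancy. The matter is therefore one of safety for participants and contacts. It has no bearing on the statistical design.

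**Working it through.** The check compares stated intervals. No power or sample-size formula is involved.

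**Inputs**

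- Wait required before recall, either disease: 4 days from rash (section on measles or rubella diagnosis).
- End of the measles contagious period: 4 days from rash (Background, Measles).
- End of the rubella shedding period: 7 days from rash (Background, Rubella).

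**Shortfall** = end of stated period - wait required, accepting the last stated day as the first permitted day for both diseases, as the protocol does for measles.

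- Measles: 4 - 4 = 0 days. The rule matches its apparent source.
- Rubella: 7 - 4 = 3 days, so recall on days 4, 5 and 6 passes the test too early. The gap is largest for a child seen on day 4 and closes for one seen on day 7.

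**Boundary.** If the last stated day were itself counted as infectious, the waits would be 5 days for measles and 8 for rubella, with shortfalls of 5 - 4 = 1 and 8 - 4 = 4 days. The rubella excess over measles is 3 days on either convention.

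**Effect of a 7-day rubella wait on visit timing.** Let T be the target visit date and R the date of rash onset. This assumes that the follow-up visit is the scheduled one and has not yet taken place; the protocol does not say so.

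- 9-month visit, with return allowed "as long as their age is 9 months, +/- 7 days" (stated for temporary exclusions), so the latest date is T+7. With 4 days: R + 4 <= T + 7, so R <= T+3. With 7 days: R + 7 <= T + 7, so R <= T. Newly outside: R = T+1, T+2, T+3, which is 3 onset dates.
- Per-protocol set, which requires that infants "Have adequate blood specimen for serological analysis from each visit within 3 days of 6, 9 and 11 months of age", so the latest date is T+3. With 4 days: R + 4 <= T + 3, so R <= T-1. With 7 days: R + 7 <= T + 3, so R <= T-4. Newly outside: R = T-3, T-2, T-1, which is 3 onset dates for each of the 9- and 11-month visits.

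The protocol gives no rubella incidence for the study area, so these dates cannot be turned into an expected number of infants.

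**The case against.** The strongest reply is that the duty placed on staff is to ensure the child is non-infectious, and the 4 days are only a minimum. Staff who thought a rubella case still infectious on day 5 would be expected to wait. On this view the text is under-specified for rubella and does not direct early recall. That is fair, and it lowers the weight of the point. It does not remove the mismatch, because the bracket is the only test staff are given and day 4 passes it.

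Other points also stand in part:

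- **Shedding is not the same as infectiousness.** The measles statement concerns contagiousness. The rubella statement concerns possible shedding, with infectiousness greatest when the rash erupts, and the Background also describes rubella as less infectious than measles. A reader might infer that a child with rubella is definitely infectious on days 4 to 6. The protocol does not say that; 7 days is a cautious outer limit.
- **The rule covers only part of the exposure.** The Background puts rash in 50-80% of rubella infections and has shedding begin 7 days before it. No wait counted from rash can address that part. This limits the benefit of the change, but a rule that exists should still match its stated basis.
- **Diagnosis may come late.** The protocol states: "No clinical laboratory evaluations will be offered in this study". Confirmation would come from outside the study, and delay could use up the 3 days. This cannot be relied on, since the recall sentence requires a diagnosis without repeating the need for laboratory confirmation.
- **Nothing can now be prevented in this cohort.** The assay change is introduced with "Since the inception of the project and completion of the field data collection a newer assay", which indicates that field work is finished. This limits the action to the text and to reuse.

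**Conclusion.** The point holds as a minor one. For rubella, the stated wait is up to 3 days shorter than the protocol's own shedding period; for measles there is no shortfall. This rests on accepting the last stated day as the first permitted day, and on treating the shedding period as the cautious basis for a site-visit rule.

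Three stronger readings are not supported:

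- **That anyone was exposed or harmed.** The protocol reports no recalled rubella case and does not describe clinic scheduling or separation of patients. Contact with a susceptible person is an assumption. Nor can the problem be called rare on a rubella figure: the analysis section's remarks on recent local disease concern measles only.
- **That the trial's results are affected.** Sample size, endpoints and analysis methods do not depend on this rule.
- **That a longer wait could never cost the primary analysis an infant.** The primary analysis requires that infants "Have adequate blood specimen for serological analysis from study site visits at 6, 9 and 11 months of age" and sets no day limit of its own. It also requires receipt of the assigned MR dose or doses. If the 9-month window were enforced and the dose withheld, the infant would be lost.

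**What to change.** Split the bracketed test by disease: keep a wait of at least 4 days from rash for measles and require at least 7 days for rubella. The sponsor's clinicians should confirm the exact boundary, including whether day 7 itself is acceptable.

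The cost is one sentence in the protocol and in any SOP that carries the rule. The earliest rubella recall moves from day 4 to day 7. In rare cases that could take a scheduled visit outside the 9-month window or the 3-day per-protocol limit, for the onset dates worked out above. The existing visit-window and analysis-set rules should apply unchanged; this correction gives no reason to relax them.

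With field collection apparently complete, the change applies to the protocol text and to any SOP carried into another study.
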